#### **6.2.2. Change from baseline in hematological laboratory parameters, including hemoglobin, reticulocytes, lactate dehydrogenase, and unconjugated bilirubin.**

Descriptive statistics (Section 5.3) for each parameter will be presented at baseline and each evaluation post baseline. Change from baseline for each post baseline evaluation will also be presented.

Mean (SD) for both raw values and change from baseline values will be plotted over time. These figures will be presented for each parameter separately.

### 6.2.3. Incidence of SCD-related AEs

Treatment-emergent SCD-related AEs will be summarized as follows (additional details in Section 6.1.1).

- Treatment emergent SCD-related AEs by SOC and PT
- Treatment-related treatment emergent SCD-related AEs by SOC and PT
- Treatment emergent SCD-related Serious AEs by SOC and PT
- Treatment-related treatment emergent SCD-related Serious AEs by SOC and PT

### 6.3. Exploratory Endpoints

#### 6.3.1. Change from baseline in adhesion of whole blood to microfluidic channels.

Descriptive statistics (Section 5.3) will be presented at baseline and each evaluation post baseline. Change from baseline and percent change from baseline for each post baseline evaluation will also be presented.

Mean (SD) of raw observed values will be plotted over time separately for the following parameters:

- result from whole blood flow adhesion on Vascular Cell Adhesion Molecules (VCAM) (cells/mm^2)
- result from whole blood flow adhesion on P-selectin (cells/mm^2).

#### 6.3.2. Change from baseline in RBC sickling from peripheral blood smears.

Descriptive statistics (Section 5.3) will be presented at baseline and each evaluation post baseline. Change from baseline and percent change from baseline for each post baseline evaluation will also be presented.

For baseline, the first available record within the nominal visit (Day 1) will be used. All other records from this nominal visit will not be used in analysis. For post-baseline records, the average of all assessments that belong to same nominal visit will be used.

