g In selected regions, qualitative interviews with English speaking participants will be conducted during the Screening period and may include multiple interviews.

h Drug accountability to be completed if baseline visit is on the same day as EOT assessments from the originating study.

i Contraception check for reproductive age males or females of child-bearing age.

j Samples to be obtained predose for all visits.

k Participants should return to the study site for an EOS visit approximately 12 weeks after the last dose of study drug.

l Exploratory biomarkers may include markers of hemolysis such as levels of haptoglobin, hemopexin, and soluble C3.

Note: Eligible participants will receive open-label osiveltor on Day 1 (Baseline Visit). It is intended that Day 1 coincides with the final visit from the originating osiveltor study. EOT assessments from the originating study will serve as Baseline assessments for this study. If Day 1 for this study is greater than 7 days from the completion of the originating study, new Baseline assessments will be obtained. Additional assessments that may not have been included in the prior EOT assessments will need to be completed at the Day 1 visit prior to study drug administration.

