#### 3.3.2. Change from baseline in RBC sickling from peripheral blood smears.

% sickled cells will be derived from the parameters obtained from the blood smear using the following equation:

$$\frac{\text{total number of sickled cells per slide}}{\text{total number of cells per slide}} \times 100\%$$

Rules for defining baseline are described in Appendix 1.2.

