#### 6.3.3. Change from baseline in RBC deformability.

Descriptive statistics (Section 5.3) will be presented at baseline and each evaluation post baseline. Change from baseline and percent change from baseline for each post baseline evaluation will also be presented.

For baseline, the first available record within the nominal visit (Day 1) will be used. All other records from this nominal visit will not be used in analysis. For post-baseline records, the average of all assessments that belong to same nominal visit will be used.

Mean (SD) of raw observed values will be plotted over time for the following parameters: PoS, EImax (oxyscan only), EImin.

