**Table 4: Analysis visit windows for participants with delayed start: EPO, pharmacodynamic endpoints and PROs**

Analysis Visit Time	Target Study Day	Per Protocol Study Day Range	Study Day Range for Statistical Analysis*
Baseline visit	1	[-29, 31]	[**, 1]
Week 12	84	[77, 91]	[42, 126]
Week 24	168	[161, 175]	[127, 210]
Week 36	252	[238, 266]	[211, 294]
Week 48	336	[322, 350]	[295, 378]
Week 60	420	[406, 434]	[379, 462]
Week 72	504	[490, 518]	[463, 546]
Week 84	588	[574, 602]	[547, 630]
Every 12 weeks	672	[658, 686]	...
.....			

Pharmacodynamic endpoints include RBC deformability, flow adhesion and blood smear.

\*If multiple assessments occur within a visit window, then the average of those assessments will be used for summarization and analysis. For PROs and pharmacodynamic endpoints, if multiple assessments occur within a visit window, the assessment before or on the target study day will be used for summarization and analysis.

\*\* Refer to Appendix 1.2 for baseline derivation rules

**Table 5: Analysis visit windows for participants without delayed start: vital signs, EPO, pharmacodynamic endpoints, PROs, labs (hematology and chemistry)**

Analysis Visit Time	Target Study Day	Per Protocol Study Day Range	Study Day Range for Statistical Analysis*
**Baseline visit	NA	NA	NA
Week 12	84	[77, 91]	[42, 126]
Week 24	168	[161, 175]	[127, 210]
Week 36	252	[238, 266]	[211, 294]
Week 48	336	[322, 350]	[295, 378]
Week 60	420	[406, 434]	[379, 462]
Week 72	504	[490, 518]	[463, 546]
Week 84	588	[574, 589]	[547, 630]
Every 12 weeks	672	[658, 686]	...
...			

Pharmacodynamic endpoints include RBC deformability, flow adhesion and blood smear.

\*If multiple assessments occur within a visit window, then the average of those assessments will be used for summarization and analysis. For PROs and pharmacodynamic endpoints, if multiple assessments occur within a visit window, the assessment before or on the target study day will be used for summarization and analysis.

\*\* This is taken from the Week 12 EOT analysis visit (See Appendix 1.2) from C5351004 parent study.

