## **Appendix 1.2. Baseline Derivations**

### **Baseline derivation for labs, EPO, pharmacodynamic endpoints, weight and vital signs**

1. If the gap between EOT visit (EOT CRF form) from parent study and study day 1 from OLE study is  $< 7$  days (date of first dose of study drug in OLE – EOT visit date from parent study + 1  $< 7$ ), use Week 12 analysis visit assessment from the parent study to serve as the baseline. If this assessment is not available, baseline is set to missing.
2. If the above defined gap in #1 is  $\geq 7$  days, use the latest pre-dose day 1 assessment from OLE study to serve as the baseline.

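### RBC sickling and RBC deformability have two incompatible baseline rules in the SAP, and replicate records are handled differently at baseline and follow-up

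*SAP*

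**What the plan says.** **Definitions.** SAP 3.3.2 (sickling) and 3.3.3 (deformability) both defer: "Rules for defining baseline are described in Appendix 1.2". That appendix is headed "Baseline derivation for labs, EPO, pharmacodynamic endpoints, weight and vital signs", and the notes to SAP Tables 4 and 5 settle its scope: "Pharmacodynamic endpoints include RBC deformability, flow adhesion and blood smear". With a gap under 7 days it takes the parent Week 12 analysis visit and sets baseline to missing if that value is absent. With a gap of 7 days or more the instruction is to "use the latest pre-dose day 1 assessment from OLE study to serve as the baseline".

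**Analysis sections.** SAP 6.3.2 and 6.3.3 carry their own paragraph: "For baseline, the first available record within the nominal visit (Day 1) will be used", followed by "All other records from this nominal visit will not be used in analysis". Neither makes an exception for short gaps. For follow-up: "For post-baseline records, the average of all assessments that belong to same nominal visit will be used".

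**Visit-window tables.** The Table 5 footnote takes baseline from the parent Week 12 EOT visit for all participants without a delayed start, that is, gaps up to 42 days. The footnotes to Tables 4 and 5 also say that, when a pharmacodynamic endpoint has several assessments in one study-day window, the one on or before the target day is used.

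**Protocol.** The note to Table 2 says "EOT assessments from the originating study will serve as Baseline assessments for this study", and calls for new baseline assessments only when Day 1 falls more than 7 days after the parent study ends. Table 2 nevertheless marks smear and deformability at the Baseline visit, with pre-dose sampling at every visit.

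**The concern.** Both endpoints are reported as change and percent change from baseline, so the choice of baseline enters every result. The SAP does not say which rule prevails. Two programmers working from the same document could produce different change scores and different numbers of participants with data, and the choice could end up being made after the data are seen. Flow adhesion, the third pharmacodynamic endpoint, has no such paragraph in SAP 6.3.1 and follows Appendix 1.2 alone, so assays taken at the same visit could have different baselines.

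Separately, SAP 6.3.2 and 6.3.3 set one baseline record against an average at follow-up. If replicates exist, that adds avoidable measurement error to the change, and percent change divides by the noisier of the two values.

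**Working it through.** The plan states no figure on this point, so there is none to reproduce. Two checks follow.

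**1. Which record each rule selects.** Let d be the days from the parent EOT date to the first extension dose. The SAP defines the gap as d + 1. I take the protocol's completion of the parent study to be the EOT date.

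| d (days) | SAP gap | Appendix 1.2 | Table 4 or 5 baseline note | SAP 6.3.2/6.3.3 | Protocol note: new baseline required? |
|---|---|---|---|---|---|
| 0–5 | 1–6 | Parent Week 12, else missing | Parent Week 12 | First extension Day 1 record | No |
| 6–7 | 7–8 | Latest pre-dose Day 1 | Parent Week 12 | First extension Day 1 record | No |
| 8–41 | 9–42 | Latest pre-dose Day 1 | Parent Week 12 | First extension Day 1 record | Yes |
| 42 or more | 43 or more | Latest pre-dose Day 1 | Refers to Appendix 1.2 | First extension Day 1 record | Yes |

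- Gap under 7: the rules use different studies. A participant whose only sample is filed under the parent visit has a baseline under Appendix 1.2 and none under 6.3.2/6.3.3. A participant with a Day 1 sample but no parent Week 12 value has the reverse.
- Gap 7 or more: both use extension Day 1, but one takes the *first* record and the other the *latest* pre-dose record. They agree if there is one record and differ if there are more. The clause discarding other Day 1 records shows that the SAP allows for more than one.
- Gap 7 to 42: Table 5 contradicts Appendix 1.2 as well, so referring 6.3.2/6.3.3 to Appendix 1.2 would not by itself leave a single rule.

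**2. Replicate error.** Assume k independent replicates per visit, each with error variance s². Neither k nor s is in the documents, so k = 1 to 4 is an assumed range.

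- One baseline record against a follow-up mean: s²(1 + 1/k)
- Mean against mean: 2s²/k
- SD ratio: √[(1 + 1/k) / (2/k)] = √[(k + 1)/2]

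| k | One against mean (s²) | Mean against mean (s²) | Variance ratio | SD ratio |
|---|---|---|---|---|
| 1 | 2.00 | 2.00 | 1.0 | 1.00 |
| 2 | 1.50 | 1.00 | 1.5 | 1.22 |
| 3 | 1.33 | 0.67 | 2.0 | 1.41 |
| 4 | 1.25 | 0.50 | 2.5 | 1.58 |

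This asymmetry comes from 6.3.2/6.3.3 alone. Under the Table 4/5 rule a single follow-up assessment is selected and the asymmetry does not arise. The size therefore depends on a second unresolved conflict. SAP 5.1 exempts only PK from the windows, so it does not resolve that conflict in favour of nominal visits.

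**The case against.** Four points can be made against the concern.

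- **The schedule covers it.** A reader might infer that direct roll-overs as a group would lose their baseline under 6.3.2/6.3.3. The documents do not support that. Protocol Table 2 schedules both assays at Baseline for participants without a delay, while leaving hematology and chemistry blank there, and its note requires assessments missing from the parent EOT visit to be done on Day 1. A missing Day 1 record is possible, because parent EOT assessments may stand as Baseline, but it is not the scheduled path. Appendix 1.2 can also create missing baselines, and whether Part A collected these assays at Week 12 cannot be checked here.
- **The override may be deliberate.** SAP 2.2 says the presentation of exploratory endpoints may be modified in Section 6.3. That permits a different presentation. It does not say that a different baseline prevails, and 3.3.2/3.3.3 still point to the appendix.
- **The SD ratios may not apply.** A reader might take 1.22 or 1.41 as the inflation of the reported SD of change. That is not supported: no replicate number is given, each visit shows a single scheduled collection, and the ratios cover replicate error only. Variation between participants and between visits is unchanged, so the reported SD would rise by less.
- **The stakes are low.** Both endpoints are exploratory, descriptive and collected only where available. This stands.

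**Conclusion.** The contradiction holds on the text: two baseline rules for the same two endpoints, with no statement of precedence. For gaps under 7 days they use different studies, and either can leave a participant without a change score that the other would give. For longer gaps they differ only when Day 1 has more than one pre-dose record. How many participants are affected cannot be derived from the documents.

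The replicate asymmetry is conditional. It needs k above 1 and 6.3.2/6.3.3 to prevail over the Table 4/5 footnotes. The replicate-error SD ratio is then 1.22 at k = 2 and 1.41 at k = 3, assuming independent replicates of equal variance; at k = 1 it is 1.00. It is a loss of precision, with no clear direction of bias in the absolute change.

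No hypothesis is tested, and the primary and secondary results are unaffected.

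**What to change.** 1. Replace the baseline paragraph in SAP 6.3.2 and 6.3.3 with one rule based on Appendix 1.2.
2. Add a fallback: when the gap is under 7 days and the parent Week 12 value is missing, use the pre-dose extension Day 1 sample. Report how many baselines come from each source.
3. Correct the Table 5 baseline footnote so that gaps of 7 to 42 days follow the same rule as Appendix 1.2.
4. Apply one replicate rule to baseline (pre-dose records only) and to follow-up visits. The mean of same-visit replicates is preferable; it would replace the choice of the latest record within the selected baseline visit. Align the Table 4 and 5 footnotes with it, and state whether follow-up visits are defined by nominal visit or by study-day window.

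The cost is SAP wording and a small programming change, with no new data collection. It should be done before these endpoints are analysed.

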#### 6.3.3. Change from baseline in RBC deformability.

Descriptive statistics (Section 5.3) will be presented at baseline and each evaluation post baseline. Change from baseline and percent change from baseline for each post baseline evaluation will also be presented.

For baseline, the first available record within the nominal visit (Day 1) will be used. All other records from this nominal visit will not be used in analysis. For post-baseline records, the average of all assessments that belong to same nominal visit will be used.

Mean (SD) of raw observed values will be plotted over time for the following parameters: PoS, EImax (oxyscan only), EImin.

#### 6.3.4. Change from baseline in erythropoietin levels.

Descriptive statistics (Section 5.3) of baseline, each evaluation post baseline and change from baseline will be provided for observed and log-transformed erythropoietin values, respectively.

Mean (SD) for both log-transformed erythropoietin values and corresponding change from baseline values will be plotted over time.

### 6.3.5. Patient-Reported Outcome Endpoints

- **PROMIS SF Fatigue 13a, PROMIS SF Pain Interference 8a and PROMIS NRS Pain intensity**

Descriptive statistics (Section 5.3) of the total raw score at each visit will be provided for each PRO. Total raw scores will be derived for PROMIS SF Fatigue 13a and PROMIS SF Pain Interference 8a.

PROMIS-1a will also be summarized categorically (Section 5.3) using n (%) under the following categories: 0 = None, 1-3 = Mild, 4-6 = Moderate, 7-10 = Severe.

All questions must be answered in order to arrive at the raw total score.

- **PGI-S, PGI-S of fatigue, and PGI-S of pain**

Data collected under different forms will be summarized separately. Summaries will include categorical frequency distribution (Section 5.3) over time.

- **CGI-S**

Summaries will include categorical frequency distribution and continuous descriptive summary statistics (Section 5.3) at each visit.

“Not assessed” category will be assigned as missing for continuous descriptive summary.

- **EuroQol EQ-5D-5L**

*Summary of VAS score:* Descriptive statistics (Section 5.3) will be provided at each visit for the VAS score.

*Summary of the 5 dimensions:* For each dimension, the number and percentage of participants in each of the 5 response levels will be presented.

*Summary of EQ-5D-5L Index:* Descriptive statistics (Section 5.3) will be provided at each visit for the index value.

- **WPAI+CIQ:SCD**

- Number of participants employed, total number of hours missed from work because of problems associated with SCD, total number of hours missed from work due to other reasons and total number of hours worked will be summarized descriptively (Section 5.3) by visit.
- Descriptive summary statistics (Section 5.3) for the observed SCD work productivity score will be presented at each visit.

- Number of participants who attend classes in an academic setting, total numbers of hours missed from class/school because of problems associated with SCD, total numbers of hours actually attended class/school will be summarized descriptively (Section 5.3) by visit.
- Descriptive summary statistics (Section 5.3) for the observed SCD regular daily activity score will be presented at each visit.
- Descriptive summary statistics (Section 5.3) for the observed SCD school productivity score will be presented.

### 6.3.6. Pharmacokinetic Concentration Data

Whole blood and plasma concentrations of osivelotor will be listed using the safety analysis set and summarized using the PK analysis set for each time point and visit. Summaries will include n, arithmetic mean, SD, coefficient of variation (CV) %, geometric mean (GM), geometric CV %, median, minimum and maximum.

In summary tables, concentrations below the limit of quantification (BLQ) will be set to zero. In listings BLQ values will be reported as "<LLQ", where LLQ will be replaced with the value for the lower limit of quantification.

In summary tables, statistics will be presented for a particular dose when  $\geq 3$  evaluable measurements are available for a given timepoint and dose group. Only minimum and maximum values will be presented when  $< 3$  evaluable measurements are available for a given timepoint and dose group.

### 6.4. Subset Analyses

No subset analyses are planned for this study.

### 6.5. Baseline and Other Summaries and Analyses

#### 6.5.1. Baseline Summaries

Demographic data, baseline characteristics, SCD history and VOC history (overall and by dose group) will be summarized using descriptive statistics (Section 5.3).

Historical SCD complications and concurrent SCD complications will be summarized.

For medical history, counts and percentages will be provided at the participant-level and any multiple occurrences in a participant for any given term will be counted only once.

#### 6.5.2. Study Conduct and Participant Disposition

The number of participants screened based on all participants who signed informed consent, screen failures (n (%)) with percentage based on total participants screened and reasons for screen failure (n (%)) with percentages based on total number of screen failures) will be summarized for all screened participants only.

The following summaries will be presented for disposition by dose arm and overall:

- Number (%) of participants treated

- Number (%) of participants completing treatment
- Number (%) completing study
- Number (%) of participants who discontinue study or discontinue treatment along with primary reason for discontinuation

Number (%) of participants in each analysis set will be summarized in a separate table.

### 6.5.3. Protocol Deviations

A summary of major protocol deviations (Section 5.3) as assessed by the study team will be provided.

### 6.5.4. Study Treatment Exposure

Duration of exposure (in weeks) will be summarized (Section 5.3).

Duration of exposure (in weeks) to study drug is defined as the number of weeks from initiation of study drug to the end of study drug treatment (refer to Section 5.1). If treatment end date is missing, then the data cut-off date will be used.

It is defined as below:

$$\text{Duration of exposure (weeks)} = \frac{(\text{Date of last dose} - \text{Date of first dose} + 1)}{7}$$

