## **7.3. Randomization and Blinding**

This is an open-label study. Randomization and blinding are not applicable.

As this is an open-label, long-term extension study, the sponsor may conduct unblinded reviews and/or summaries of the data during the course of the study for the purpose of safety assessment, supporting clinical development, and/or supporting regulatory review.

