## 2. INTRODUCTION

This statistical analysis plan (SAP) provides the detailed methodology for summary and statistical analyses of the data collected in Study C5351005.

The primary analysis for this study will occur after all enrolled participants have completed End of Study (EOS) visit or have discontinued the study.

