#### 5. GENERAL METHODOLOGY AND CONVENTIONS

##### 5.1. Definition and Terminology

- Day 1 is the day of first dose of C5351005 study drug administration.
- EOT information is collected on the C5351005 EOT eCRF page. The EOT date from this form will serve as the last dose of study (eg for defining TEAE etc).
- Date of study completion/discontinuation is the study completion/discontinuation date from C5351005 EOS eCRF page. If this date is missing, date of last known assessment will be used.
- Study Day is defined relative to the C5351005 date of first dose of study drug, i.e., Day 1.

For study assessments or events that occur on or after the date of first dose of study drug, the study day of an assessment/event is calculated as:

Study Day = event date – date of first dose + 1.

For pre-treatment events, the study day is calculated as:

Study Day = event date – date of first dose.

- Study Visit is the nominal visit as recorded on the CRF.
- Visit windows rules are defined in Appendix 1. No windowing rules will be applied to PK endpoints where only nominal visits will be used for presentation purposes.
- Treatment of Outliers for Pharmacokinetic Data

Individual blood and plasma concentration-time points, if considered anomalous, may be excluded from the analysis at the discretion of the pharmacokineticist following a review of the available documentation.

Entire individual treatment profiles for any participant, if considered anomalous, may be excluded following review of the available documentation and discussion with the Sponsor. However, results of analysis with and without the excluded profiles may be presented in the CSR.

Any such exclusion or treatment of anomalous PK data, as described above, will be discussed with the Sponsor's Clinical Pharmacologist and clearly described in the CSR along with justification for exclusion.

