### **6.2. Secondary Endpoint(s)**

#### **6.2.1. Annualized rate of VOC**

The summary and analyses of on-treatment VOCs will include the following:

- Duration of on-treatment period (weeks)
- Total participant-years

- Total number of VOCs
- Total number of uncomplicated VOCs
- Total number of complicated VOCs and total for each type (ACS, hepatic sequestration, splenic sequestration, priapism)
- Number of participants with VOCs
- Number of VOCs per participant
- Number of uncomplicated VOCs per participant
- Number of complicated VOCs per participant
- Annualized incidence rate of VOC
- Annualized rate of VOC along with 95% CI (using Negative Binomial Model described below)

A listing of VOC data will be provided.

Multiple VOC events will be counted per participant. Both complicated and uncomplicated VOC events will be included for the calculation of the VOC rate.

**Annualized incidence rate of VOC on-treatment** will be calculated at the group level using the formula below:

$$\text{Annualized Incidence Rate of VOC on – treatment} = \frac{\text{sum of number of events on – treatment}}{\text{sum of participant years on – treatment}}$$

where participant years on-treatment for each participant = (EOT date – date of first dose of study drug+1)/365.25. EOT date is the last known treatment date from the EOT page in CRF.

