## 7. INTERIM ANALYSES

Not applicable

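### SAP 6.5.4 fills a missing treatment end date with the data cut-off date, although nobody is still on drug at the only planned analysis, so exposure would be overstated for anyone whose date stays missing

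*SAP*

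**What the plan says.** SAP 6.5.4 sets the quantity up this way: "Duration of exposure (in weeks) to study drug is defined as the number of weeks from initiation of study drug" to the end of treatment, calculated as (last dose date − first dose date + 1)/7. It then adds: "If treatment end date is missing, then the data cut-off date will be used". No condition limits this to participants still on treatment, and the SAP does not define the data cut-off date.

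On timing, SAP 2 states: "The primary analysis for this study will occur after all enrolled participants have completed End of Study (EOS) visit or have discontinued the study". SAP 7, on interim analyses, reads "Not applicable".

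The neighbouring date rules are these:

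- **Last dose date, SAP 5.1:** "The EOT date from this form will serve as the last dose of study (eg for defining TEAE etc"). No fallback is given if the date is missing.
- **VOC participant-years, SAP 6.2.1:** "EOT date is the last known treatment date from the EOT page in CRF". Again there is no fallback.
- **Study completion or discontinuation date, SAP 5.1:** "If this date is missing, date of last known assessment will be used".

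Protocol 8.2 lists loss to follow-up among the reasons for discontinuing study drug. Protocol 7.4 provides a dose diary, whose details are entered in the eCRF, and a count of remaining drug at each visit.

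**The concern.** Carrying treatment forward to a cut-off is reasonable when an empty end date means that dosing continues. At the analysis planned here it cannot mean that. An empty end date then means that the participant has stopped and the date is unknown or was not entered. Filling it with the cut-off date credits treatment time after the participant stopped, and the error runs in one direction only.

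The result can also be incoherent within a participant. If the study discontinuation date is known, or is filled with the last assessment under SAP 5.1, the derived treatment period can end after the derived study period.

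What is at stake is the exposure summary itself. Protocol 3.3 gives additional patient-years of exposure as a reason for the study. SAP 5.3 splits the summaries by dose and by delayed start, so a few filled dates could move a small cell noticeably.

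**Working it through.** The plan states no exposure figure, so there is none to reproduce. The check has two parts.

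**1. Who can the rule apply to?** By SAP 2, every participant has completed the end-of-study (EOS) visit or discontinued before the analysis. By SAP 7, there is no earlier planned analysis. So the number still on drug at the planned analysis is zero, and every use of the rule falls on someone who has stopped.

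**2. How large is the excess for one participant?** Applying the SAP 6.5.4 formula twice, with Day 1 as the first dose:

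excess (weeks) = (cut-off day − true last-dose day)/7

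Input from the documents: the EOS visit is about 12 weeks (84 days) after the last dose (Protocol 5.1).

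Assumed inputs:

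- The cut-off is the EOS visit of a last finisher who started on the same calendar date. With a last dose at Week 84, that is day 588 + 84 = 672. With a last dose at Week 96, it is day 672 + 84 = 756.
- The true stop is at Week 12, 24, 48 or 72.

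| True last dose | True exposure | Credited, cut-off day 672 | Excess | Credited, cut-off day 756 | Excess |
|---|---|---|---|---|---|
| Day 84 | 12.0 wk | 96.0 wk | 84.0 wk | 108.0 wk | 96.0 wk |
| Day 168 | 24.0 wk | 96.0 wk | 72.0 wk | 108.0 wk | 84.0 wk |
| Day 336 | 48.0 wk | 96.0 wk | 48.0 wk | 108.0 wk | 60.0 wk |
| Day 504 | 72.0 wk | 96.0 wk | 24.0 wk | 108.0 wk | 36.0 wk |

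Even if the cut-off fell on the participant's own EOS visit, the excess would be about 84/7 = 12 weeks.

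**Effect on an arm mean.** Assume n participants, m of them with a missing date. The others have 84 weeks; the m have 24 true weeks and 96 credited weeks.

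- True mean = [(n − m) × 84 + m × 24]/n
- Reported mean = [(n − m) × 84 + m × 96]/n
- Shift = 72m/n

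| n | m | True mean | Reported mean | Change |
|---|---|---|---|---|
| 10 | 1 | 78.0 | 85.2 | +9.2% |
| 10 | 3 | 66.0 | 87.6 | +32.7% |
| 20 | 2 | 78.0 | 85.2 | +9.2% |
| 35 | 1 | 82.3 | 84.3 | +2.5% |
| 35 | 3 | 78.9 | 85.0 | +7.8% |

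In each of these cases the median stays at 84 weeks. The range changes from 24–84 to 84–96 weeks, so the short exposures disappear from the table.

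**The case against.** A reader might infer that the cut-off date also dilutes the safety rates and stretches the treatment-emergent window. The documents do not support that:

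- **Adverse event percentages** use the number of participants in the column as denominator (SAP 5.3.1), and no exposure-adjusted adverse event rate is planned.
- **VOC participant-years and the window of last dose plus 56 days** take the end-of-treatment (EOT) date from its CRF page. The cut-off sentence stands only in SAP 6.5.4. For those two uses the documents show only that no fallback is stated, which is a gap and not a bias.

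Four further objections deserve weight.

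- **The harm is conditional.** The EOT page asks for the last known treatment date, which can be completed for a lost participant, and the diary and drug counts give sites a source. Nothing shows that any date is or will be missing. This stands.
- **The contrast with SAP 5.1 is not a contradiction.** The last-assessment rule there concerns the study end date, a different variable. This stands. It remains true that the two rules together can place the end of treatment after the end of study.
- **A last-assessment fallback has its own bias.** If the last assessment is the EOS visit, exposure would still be overstated by about 12 weeks. This stands and shapes the fix.
- **The sentence may be meant for earlier data summaries.** Protocol 7.3 says that "the sponsor may conduct unblinded reviews and/or summaries of the data during the course of the study", and a cut-off rule would be normal there for ongoing participants. This may explain the sentence, but the SAP plans no such summary and sets no such limit.

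**Conclusion.** The point holds as a mismatch between the rule and the timing of the only planned analysis. For any participant whose EOT date stays missing, SAP 6.5.4 would overstate duration of exposure. The amount depends on the cut-off date and the true stop date. Neither is given, and nor is the number of missing dates or the size of the arms, so every figure above is an illustration. Under those assumptions the excess runs from about 12 to 96 weeks per participant, and the shift in an arm mean from 2.5% to 32.7%. If no date is missing, the effect is nil.

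The consequence is confined to a descriptive summary. The primary-endpoint percentages and the VOC rates are not shown to be affected. The change is still worth making before the analysis, because the rule as written has no proper use there and can err only upward.

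**What to change.** Replace the sentence in SAP 6.5.4 with an ordered rule:

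1. If the treatment end date is missing, use the last documented dose date from the diary or drug accountability records (Protocol 7.4).
2. If there is none, use the last known on-treatment visit or assessment. Exclude the EOS follow-up visit, and cap the date at the study discontinuation date.
3. Use the data cut-off date only for participants confirmed as still on treatment in an earlier data summary, and define that date.
4. Report how many dates were imputed, and by which step.
5. Place the rule in SAP 5.1, so that the same date serves exposure, the treatment-emergent window and VOC participant-years. This also closes the missing fallback for the last two.

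The cost is a few SAP sentences and no new data collection. The step 2 date remains somewhat imprecise, and reported exposure may be lower.
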